17.9 PHARMACOKINETIC MEASURES AND EVALUATION

17.9.1 TIMING OF PHARMACOKINETIC BLOOD SAMPLING

For the time schedules of PK blood samples, please refer to [Section 17.8.1](#).

17.9.2 PHARMACOKINETIC SAMPLE HANDLING AND SHIPMENT

Methods of PK sample collection are described in [Section 7.2.2.1.2](#). Further instructions for sampling procedures, and for handling, storage and shipment of the samples will be provided in the Laboratory Manual in the ISF.

17.9.3 PHARMACOKINETIC DATA EVALUATION

For PK analysis and displays, concentrations will be presented in the same format as reported in the bioanalytical report. Only concentrations within the validated concentration range and actual sampling times will be used for the calculation of PK parameters.

17.9.4 HANDLING OF MISSING BIOANALYTICAL DATA

In the noncompartmental analysis, concentration data identified as no sample available (NOS), no valid results (NOR), or not analyzed (NOA) will not be considered. Below limit of quantification (BLQ) and NOP values in the lag phase will be set to zero. The lag phase is defined as the period between time zero and the first timepoint with a concentration above the quantification limit. All other BLQ and/or NOP values of the profile will be ignored. Every effort will be made to include all concentration data in an analysis. If not possible, a case to case decision is required whether the value should be excluded.

Descriptive statistics of concentrations will be calculated only when at least 2/3 of the individuals have concentrations within the validated concentration range. The overall sample size to decide whether the '2/3' rule is fulfilled will be based on the total number of samples intended to be drawn for that time point (i.e., BLQ, NOR, NOS, NOA, NOP are included). Descriptive statistics of parameters are calculated only when at least 2/3 of the individual parameter estimates of a certain parameter are available.

18 REVISION HISTORY

18.1 SUMMARY OF CHANGES

Protocol Version 4.0 dated 15MAY2020

Replaces: Protocol Version 3.0 dated 31JAN2020

[figure not shown]
The following table describes changes from Version 3.0 (dated 31JAN2020) with justifications provided.

Section	Description	Justification
Throughout	Protocol version update. Previously read: V3.0_31JAN2020 Now reads: V4.0_15MAY2020	Version control.
Throughout	Minor grammar and content updates.	Minor grammar/content updates for clarity/accuracy of content.
Table of Contents	Minor content updates.	Minor updates required to reflect revised content.
Protocol Summary: Precis; 4.1; 7.3.4.1; 7.3.6; 15	Removal of text indicating that subjects who achieve disease control will be offered participation in a follow on, open-label 12-month treatment study (AKST4290-222).	The Sponsor decided to close AKST4290-222 study; therefore, subjects will now complete EOT procedures and a 14-days Safety Follow-up call.
Protocol Summary: Subject Participation; Schematic of Study Design; 4.1; 5.3	Previously read: Approximately 1 to 3 weeks (until disease control). Now reads: Approximately 1 to 5 weeks (inclusive of the Safety Follow-up call).	Subject participation clarified to show all subjects will now complete EOT procedures and a 14-days Safety Follow-up call because study AKST4290-222 was closed by the Sponsor; therefore, rollover to the follow-on study is not possible.
5.2	Previously read:   Exclusion Criterion #11: Subjects taking warfarin (see Section 17.6.1). Now reads: 	Updated criteria based on findings from the clinical drug-drug interaction study.

	
Criterion was removed.
 
[REDACTED]
	Updated criteria based on findings from the clinical drug-drug interaction study.
	
Now reads:
 
Criterion was removed.
 
Previously read:
 
[REDACTED]
	Updated criteria based on findings from the clinical drug-drug interaction study.
	
Now reads:
 
Criterion was removed.
 
Previously read:
 
[REDACTED]
	Updated criteria based on findings from the clinical drug-drug interaction study.
	
Now reads:
 
Criterion was removed.
 
Previously read:
 
[REDACTED]
	Updated criteria based on findings from the clinical drug-drug interaction study.
	
Now reads:
 
Criterion was removed.
 
Previously read:
 
[REDACTED]
	Updated criteria based on findings from the clinical drug-drug interaction study.
	
Now reads:
 
Criterion was removed.
 
Previously read:
 
[REDACTED]
	Updated criteria based on findings from the clinical drug-drug interaction study.

	
Now reads: Exclusion Criterion #12: Renal function as defined by estimated glomerular filtration rate (eGFR) < 45 mL/min/1.73 m² using the Modification of Diet in Renal Disease (MDRD) study equation (see Section 17.5).
 
Previously read:
 
[REDACTED]
	
	
Now reads: Exclusion Criterion #13: Use of systemic steroids (>10 mg prednisone or equivalent/day) within 14 days of first dose of study agent or known diseases (other than BP) that could require the use of systemic steroids within the study period. Subjects who have received a single high-dose of steroids (intravenous or oral) 14 days or more before the administration of the first dose of study drug are eligible for enrollment.
	Text added to clarify the window for allowed use of high-dose intravenous or oral steroids
5.4.2	Clarification added that all subjects will have EOT visit procedures and the 14-day Safety Follow-up call completed upon withdrawal.	The Sponsor decided to close AKST4290-222 study; therefore, subjects will now complete EOT procedures and a 14-days Safety Follow-up call.
7.1.1.1	Clarification to show the allowed window of use for high-dose intravenous or oral steroids. “Additionally, subjects who have received a single high-dose of steroids (intravenous or oral) 14 days or more before the administration of the first dose of study drug are eligible for enrollment. “	Text added to clarify the window for allowed use of high-dose intravenous or oral steroids
7.2.2.1, 7.3.2.1	Added “required and optional” to indicate that not all PK sampling timepoints are mandatory.	Modified to correctly describe the PK sampling time points.
7.2.2.1.1	
Previously read: As far as feasible, the following pharmacokinetic parameter will be derived by noncompartmental methods:
 
 • $C_{pre,ss,N}$ Pre-dose concentration of AKST4290 in plasma immediately before administration of the Nth dose 
In addition, the average pre-dose concentration in plasma at steady state will be calculated as the geometric mean of $C_{pre,ss,N}$ values, as applicable.
 
Now reads: As far as feasible, the following pharmacokinetic parameter will be summarized descriptively:
 
 • $C_{pre,ss,N}$ Pre-dose concentration of AKST4290 in plasma immediately before administration of the Nth dose 	Modified to correctly describe the PK parameters based on the available sampling time points.
7.5	Previously read: [REDACTED]	Updated based on findings from the clinical drug-drug interaction study.

Now reads:

15	
Note #18
 
Previously read:
 
[REDACTED]
 
Now reads:
 
[REDACTED]
	Prohibited medications and precautions modified based on findings from clinical drug-drug interaction studies.
17.6	
[REDACTED]
 
[REDACTED]
 
[REDACTED]
 
[REDACTED]
	Prohibited medications and precautions modified based on findings from clinical drug-drug interaction studies.

15, 17.8.1	
At Baseline (Visit 2) PK samples will be required to be collected pre-dose and 1 hour (± 15 minutes) after administration of the first dose. Additionally, optional PK samples may be collected at 2 hours (± 30 minutes) after administration of the first dose and 4 hours (± 30 minutes) after administration of the first dose. All PK samples collected during the scheduled weekly visits will be drawn within 1 hour prior to the morning (am) dose. At the EOT visit, the sample will be collected at any time during the visit and the time of the subject's last dose and the time of the PK sample collection will be recorded.
	
Optional time points were added to improve the evaluation of PK.

This image shows a document page with approximately 15 lines of text that have been completely redacted. The redaction is performed using thick black horizontal bars. The first bar is at the top, followed by a thin white space, then a second bar, and so on, creating a pattern of black and white horizontal stripes across the page. The redacted text is located in the upper half of the page, with the rest of the page being white space.

The image is a black and white graphic featuring a series of horizontal stripes. The stripes are of equal width and are alternately colored black and white. This pattern repeats from the top to the bottom of the frame. There are no other elements, text, or figures present in the image.

4. Abbreviations

AE(s)	Adverse Event(s)
AESI	Adverse Events of Special Interest
ATC	Anatomical Therapeutic Chemical
BP	Bullous Pemphigoid
b.i.d	Twice Daily
BPDAI	Bullous Pemphigoid Disease Area Index
BPDAI-VAS	Bullous Pemphigoid Disease Area Index Visual Analog Scale
CI	Confidence Interval
CL	Confidence Limit
CPC	Clobetasol Propionate Cream
DF	Degrees of Freedom
DLQI	Dermatology Life Quality Index
ECG	Electrocardiogram
[REDACTED]	[REDACTED]
eCRF	Electronic Case Report Form
FAS	Full Analysis Set
GCP	Good Clinical Practice
IFN-g	Interferon gamma
IgG	Immunoglobulin G
IL	Interleukin
MFC	Mometasone Furoate Cream
MoCA	Montreal Cognitive Assessment
PK	Pharmacokinetic(s)
PT	Preferred Term
SAE(s)	Serious Adverse Event(s)
SAP	Statistical Analysis Plan
SAR	Statistical Analysis Report
SD	Standard Deviation

SDTM	Study Data Tabulation Model
SE	Standard Error
SOC	System Organ Class
VAS	Visual Analog Scale
WHO	World Health Organization

5. Definitions

Adverse event surveillance period (for a subject)	Adverse events (AEs) are recorded from the time of informed consent. All AEs that occur after the first dose of study drug will be considered Treatment Emergent AEs. Subjects with Treatment Emergent AEs must be followed until the AE is resolved or is stable, unless the subject is lost to follow up.
Baseline	Visit 2 (day 1). If a measurement is performed during Visit 1 (Screening), but not Visit 2, then the measurement performed at Visit 1 is considered the baseline measurement.
BPDAI score	Either the total BPDAI activity score or the total BPDAI damage score. Both the activity score and the damage score are the arithmetic sums of their components (see Protocol section 7.1.1.3.1). For the activity score, each item in each of the lists Skin Erosions/Blisters, Skin Urticaria/Erythema/Other and Mucosa Erosion/Blisters is graded from 0 to 10 (see Protocol section 17.1 for the items and possible grades), and all items' grades are summed. The score reported in the eCRF question "Total BPDAI Activity Score" is used for analyses. For the damage score, each item in the Skin list is graded with 0 or 1 (see Protocol section 17.1 for the items), and the grades summed. The score reported in the eCRF question "Total BPDAI Damage Score" is used for analyses.
BPDAI-VAS score	The intensity of pruritus is assessed using a visual analog scale to answer the question, "How severe is your itching today?" and the subject marks an "x" on the 0- to 10-cm line where 0 is no itch and 10 is maximal itching. The degree of itching is measured as the distance in centimeters from 0, out of 10. This is repeated for the severity overall of itching in the past week and month. A total score is calculated from this out of 30 (see Protocol Section 17.2 for the items).
Incidence (of an event, among a group)	Proportion of subjects experiencing at least one event of the specified kind.
Time to disease control	Number of days from randomization to date of disease control as recorded on the eCRF.
Time to rescue therapy	Number of days from randomization to date of initial dose of rescue therapy as recorded on the eCRF.
Treatment group	Either AKST4290 or placebo.

6. Protocol summary

This is a randomized, double-blind, placebo-controlled phase 2 trial to be conducted at up to 8 sites in approximately 30 subjects to assess the therapeutic effect and safety of adjunctive AKST4290 in subjects with mild to moderate bullous pemphigoid (BP). Subjects will receive whole-body topical mometasone furoate cream (MFC) therapy (dose and dosing interval dependent upon severity of disease at time of enrollment, as assessed by the investigator) concurrently with the study agent (placebo or AKST4290 400 mg twice daily (b.i.d)) in an inpatient setting until disease control is reached (duration of inpatient stay is dependent upon individual disease course – estimated between 1–3 weeks). Study agent dosing will commence once eligibility has been confirmed and may start up to 7 days after the start of whole-body topical steroid therapy. Following clinical diagnosis, histological diagnosis of BP will subsequently be confirmed per the S2k Guideline for the Diagnosis of Pemphigus Vulgaris/Foliaceus and Bullous Pemphigoid ([Schmidt 2015](#)). Subjects will receive rescue therapy at any time if their clinical condition worsens or if their clinical condition fails to improve by the completion of Week 1 on study treatment, as assessed by the investigator. Rescue therapy will consist of whole body clobetasol propionate cream (CPC) (15-50g) and/or oral prednisone (0.5 mg/kg per day), as determined by the investigator. Subjects who receive rescue therapy will remain in the study until disease control, unless they are withdrawn or withdraw from participation.

7. Study objectives

7.1. Primary objective

To investigate the proportion of subjects who achieve disease control (defined as ≤ 3 new blisters/eczematous lesions/urticarial plaques and healing of existing blisters/eczematous lesions/urticarial plaques) following topical steroid treatment with adjunctive AKST4290 without receiving rescue therapy.

7.2. Secondary objectives

To assess the safety of AKST4290. Additional secondary endpoints include assessment of time to disease control; time to rescue therapy; change in BP Disease Area Index (BPDAl) score; and change in pruritis as assessed by the BPDAl-Visual Analog Scale (BPDAl-VAS). In addition, change in skin (biopsy) [REDACTED] counts and overall steroid dose required to achieve disease control will be assessed.

7.3. Exploratory objectives

Blister fluid protein levels [REDACTED] counts, anti-BP180 Immunoglobulin G [IgG] serum levels, serum protein levels [REDACTED] [REDACTED], and blood chemistry will be evaluated. Pharmacokinetic (PK) studies will also be conducted to assess AKST4290 plasma concentrations at various required and optional timepoints. Cognitive assessments will be performed using the Montreal Cognitive Assessment (MoCA). Quality of life will be assessed by the Dermatology Life Quality Index (DLQI). Additional biomarker evaluations may be conducted on plasma samples.

8. Study endpoints

8.1. Primary endpoint

The proportion of subjects who achieve disease control (defined as no more than (\leq) 3 new blisters/eczematous lesions/urticarial plaques and healing of existing blisters/eczematous lesions/urticarial plaques) without requiring rescue therapy.

8.2. Secondary endpoints

1. Safety as assessed by the incidence, seriousness, and severity of adverse events (AEs).
2. Time to disease control by treatment day/week.
3. Time to rescue therapy by treatment day/week.
4. Change from baseline in BPDAI score by treatment week and at disease control.
5. Change from baseline in pruritus as evaluated by the BPDAI-VAS by treatment week and at disease control.
6. Change from baseline in skin biopsy [REDACTED] levels at disease control.
7. Evaluation of total cumulative steroid exposure at baseline, by treatment week and at disease control.
8. Evaluation of maximum daily steroid dose at baseline, by treatment week and at disease control.

8.3. Exploratory endpoints

1. Change from baseline in blister fluid protein levels [REDACTED] at treatment Week 1.
2. Change from baseline in blood [REDACTED] levels by treatment week and at disease control.
3. Change from baseline in Anti-BP180 IgG levels by treatment week and at disease control.
4. Evaluations of complete blood count (CBC), blood chemistry, and serum protein levels [REDACTED] at baseline, by treatment week and at disease control.
5. Changes in AKST4290 plasma concentrations at various timepoints.
6. Change from baseline in cognitive assessments using the MoCA at disease control.
7. Change from baseline in quality of life, as assessed by the DLQI at disease control.
8. Evaluation of exploratory biomarkers in plasma samples at various timepoints.

9. Sample size

A final sample size of 30 subjects was chosen based on clinical experience.

10. General considerations for data analysis

10.1. General principles

As detailed in the protocol, the sample size of 30 subjects was chosen based on clinical experience with the intent of obtaining 27 evaluable subjects. Due to the treatment limitations, rarity of the disease, coronavirus disease 2019 (COVID-19) pandemic and expiry of Investigational Medicinal Product (IMP), enrollment ended with a total of six subjects enrolled and completing the study. Due to the reduced number of enrolled subjects, analysis described in the SAP focuses on a descriptive summary of efficacy and safety within summary tables and figures and data primarily reported in listing format. [Section 7](#) (Study Objectives) and [Section 8](#) (Study Endpoints) of the SAP present the protocol-defined study objectives and endpoints; [Section 11](#) (Summary of study population), [Section 12](#) (Safety analyses) and [Section 13](#) (Efficacy analyses) describe an abridged analytical plan relative to what was presented in the study protocol. The reduced set of planned analyses generally consists of descriptive summaries of essential study endpoints and is more appropriate given the smaller subject enrollment than was originally planned.

All summary statistics will be descriptive unless noted otherwise. Descriptive summaries will include the number of subjects (n), mean, standard deviation (SD) or standard error of the mean (SE), median, first quartile (Q1), third quartile (Q3), and range for continuous variables and number and percentages for categorical variables.

Subjects will be analyzed in the treatment group assigned at randomization for the ITT data sets. For the Safety Evaluable data set, subjects will be grouped according to actual treatment received.

10.2. Analysis datasets

10.2.1. Intent-to-Treat (ITT) Set

The full analysis set (FAS) includes the set of subjects that is as close as possible to the ideal implied by the Intention-to-treat principle. It is derived from the set of all randomized subjects by minimal and justified elimination of subjects.

10.2.2. Safety Evaluable Set

The Safety Evaluable set will include all randomized subjects who receive at least 1 dose of the study agent (placebo or AKST4290).

10.3. Data transformations and derivations

Values will be presented for all scheduled study visits according to the nominal visit obtained from the eCRF. If an unscheduled visit falls in a visit window with an existing nominal visit assessment, the nominal assessment will be used in analyses. If no nominal visit assessment exists for a visit window with unscheduled visit(s), then the first unscheduled visit within the visit window will be used.

If the End of Treatment visit is performed in place of a scheduled weekly visit, the measurements of the End of Treatment visit are also used for that scheduled weekly visit. This is assumed to be the case if the End of Treatment visit falls into the protocol-specified visit window of some scheduled visit, and that particular scheduled visit is not done.

All heights will be converted to centimeters, all weights to kilograms, and all temperatures to Celsius units.

10.4. Missing data and imputation

No explicit imputation will be used.

All partial dates will be identified, and partial dates will be imputed as follows:

- If day and month are missing but year is available, then the imputed day and month will be 01 Jan;
- If day is missing and month and year are available, then the imputed day will be the first day of the month;
- A partial date will not be imputed if the year is missing.

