5 STUDY ENROLLMENT AND WITHDRAWAL

5.1 INCLUSION CRITERIA

In order to be eligible for inclusion, all subjects must meet the following criteria:

1. Age 60-95 years, inclusive at screening.

2. Clinical diagnosis of mild to moderate BP at screening:
 - o Mild BP is defined as BPDAI \leq 10 **OR** $<$ 10% affected body surface
 - o Moderate BP is defined as BPDAI \geq 10 and \leq 55 **OR** 10%-30% affected body surface
3. Treatment naïve or initiation of whole-body high potency topical steroid treatment \leq 7 days of screening (lesion-only treatment for any amount of time with any topical steroids prior to screening is allowed without restriction).
4. Female subjects must not be pregnant or breastfeeding. Women of childbearing potential (WOCBP) must have a negative pregnancy test at screening. WOCBP and men must agree to use highly effective contraception ([Clinical Trial Facilitation Group 2014](#)) prior to study entry. A woman is considered of childbearing potential following menarche and until becoming postmenopausal (no menses for at least 1 year without an alternative cause). Should a woman become pregnant or suspect she is pregnant while she or her partner is participating in the study, she should inform her treating physician immediately. Male subjects must be willing to use a barrier method contraception while participating in the study.
5. The subject must be able to follow the study procedures, receive the treatment in the established timeframe, and agree to remain an inpatient until the end of treatment (EOT)/disease control.
6. The subject must be able to understand the procedures and agree to complete the required assessments.
7. Provide signed and dated informed consent form in accordance with local regulations and/or IRB/IEC guidelines.

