7.3.4 FOLLOW-UP

7.3.4.1 Fourteen (14)-Day Safety Follow-Up: (Day 14 ± 3) Following Discontinuation of Study Agent

All subjects will be contacted via telephone 14 days ±3 days after EOT visit to assess safety. A review of all ongoing AEs and concomitant medications will be performed.

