12.1. Adverse events

All subjects who have given informed consent will be evaluated for AEs. AEs will be reviewed, documented, and reported as required at each visit, beginning at screening. All AEs that occur after the time of treatment with the study drug will be considered Treatment Emergent AEs. All reported terms (investigator descriptions) for AEs will be encoded according to the Medical Dictionary for Regulatory Activities (MedDRA). As SAE is a type of AE, all analyses of AEs will also include SAEs.

Summaries that are displayed by system organ class and preferred terms will be ordered by descending incidence of system organ class and preferred term within each system organ class. Summaries of the following types will be presented:

- Overall summary of number of unique TEAEs and treatment-emergent SAEs and subject incidence of TEAEs meeting various criteria;
- Subject incidence of TEAEs by MedDRA system organ class and preferred term;
- Subject incidence of TEAEs by relationship to study drug, MedDRA system organ class, and preferred term

Version: 1.0

Protocol version: 4.0

At each level of summarization (eg, any AE, system organ class, and preferred term), subjects experiencing more than one TEAE will be counted only once. In the summary of TEAEs by severity grade, subjects will be counted once at the highest severity reported at each level of summarization; in the summary of TEAEs by relationship, subjects will be counted once at the closest relationship to study drug.

Adverse event data will be presented in data listings by subject, treatment group, and event. All deaths during the study will be listed by subject, to include the primary cause of death. Serious AEs and AEs leading to discontinuation of the study drug will be presented in separate data listings. A listing of AEs that qualify as adverse of special interest (AESI) will also be reported; per protocol, an AESI includes events of:

- [REDACTED]
- [REDACTED]
- [REDACTED]

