13.3. Time to Rescue therapy

Time to rescue therapy will be defined as the time to the start date of the first reported administration of steroid treatment, per the Steroid Treatment CRF, that is reported as “Rescue” for the Timing of Use variable.

For subjects who **will be positively assessed for the need of rescue therapy**, the time to rescue therapy will be calculated as:

Time to rescue therapy (days)

$$= \text{Start date of first rescue treatment} - \text{Date of Visit 2 (Baseline (Day 1))} + 1$$

In cases of **study discontinuation or a subject completing study without the need for rescue therapy**, the time will be calculated as follows:

Time to rescue therapy (days)

$$= \text{Date of study completion/discontinuation} - \text{Date of Visit 2 (Baseline (Day 1))} + 1$$

Time to rescue therapy will be presented in a listing.

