13.7. Steroid exposure

Descriptive statistics for total cumulative steroid exposure (cortisol equivalent/kg) will be summarized by treatment group. Steroid treatments will be standardized for their respective cortisol equivalent unit. To determine per kg exposure, the last subject weight reported prior to the initiation of steroid treatment (as reported by the start date) will be used. Total cumulative exposure will require assessment of the start and end date for each respective steroid treatment, in addition to the frequency reported for the treatment. Subjects that report a frequency of AS NEEDED, UNKNOWN, OTHER or INTERMITTENT will be discussed with the sponsor to determine the appropriate calculation.

A figure plotting the individual steroid exposure (cortisol equivalent/kg) per study day per subject will be presented. Steroid exposure per study day will be determined by an assessment of the start and stop dates reported for each steroid treatment on the Steroid Treatment CRF in combination with the frequency reported; daily exposure will distribute the dosing frequency evenly across the date range defined by the start and stop date for each treatment. A figure presented daily steroid exposure (cortisol equivalent/kg) will also be presented by treatment group. A listing of all steroid treatment administration will also be provided.

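### The SAP moves every partial date to the start of its month or year, so an on-treatment AE can drop out of the TEAE tables and a steroid stop can precede its start (minor)

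*SAP*

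**What the plan says.** SAP 10.4 first disclaims explicit imputation, then gives rules for partial dates. With month and year known: "If day is missing and month and year are available, then the imputed day will be the first day of the month". With only the year known, the date becomes 1 January. With the year missing, nothing is imputed. The rule does not separate start from stop dates, or AE from steroid records.

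Two analyses depend on such dates.

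- **AEs.** SAP section 5 states: "All AEs that occur after the first dose of study drug will be considered Treatment Emergent AEs". SAP 12.1 repeats the definition, and its summary tables count TEAEs only. Listings are wider: "Adverse event data will be presented in data listings by subject, treatment group, and event".
- **Steroids.** SAP 13.7 builds cumulative exposure from each record's start and end date, and for the daily figures "daily exposure will distribute the dosing frequency evenly across the date range defined by the start and stop date for each treatment".

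The one protective partial-date rule that can be read is in SAP 11.4. It presumes a medication concomitant unless the known part of its dates shows that it stopped before randomization. It covers the prior/concomitant classification and nothing else.

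**The concern.** Moving a date to the earliest day it could be is not neutral when the analysis asks whether an event came after first dose, or how long a course lasted. For AE onset the error runs one way: on-treatment events can only be moved out of the TEAE count. For a steroid stop, the imputed date can precede the recorded start, and SAP 13.7 then has no valid range over which to spread the dose. SAP 13.7 sends unclear dosing frequencies to the sponsor for discussion but says nothing about impossible date ranges.

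AE incidence and cumulative steroid exposure are both secondary endpoints (SAP 8.2), and both are in the top-line outputs (SAP 16). With six subjects, one misdated record can change a table row.

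**Working it through.** **Inputs.** The rule is from SAP 10.4. Treatment lasts 1 to 3 weeks, followed by a 14-day outpatient period (Protocol 4.1), so the windows are Day 1-7, Day 1-21 and Day 1-35. Screening is Day -3 to 0 (Protocol section 15). Assumptions: the day is missing; Day 1 is the first-dose date and is uniform over the 366 days of 2020 (seven months of 31 days, four of 30, one of 29); onset is uniform over the window; an onset dated on Day 1 itself counts as treatment-emergent. The plan gives no figure of its own to reproduce.

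**Example (illustrative dates).** First dose is 10 June. An AE on 15 June recorded as June becomes 1 June, 9 days before first dose, so it is not a TEAE. A steroid course from 10 to 24 June lasts 15 days. With the stop recorded as June, the stop becomes 1 June and the duration is 1 - 10 + 1 = -8 days.

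**AE onset, day missing.** Take an onset k days after Day 1. It is moved before first dose if it falls in the same month as Day 1 and Day 1 is not the 1st. A month of M days has M - 1 - k such Day 1 dates (zero if negative). Summed over the year, for k up to 28, the share is 1 - 12(k + 1)/366. This is linear in k, so the mean k of the window can be used.

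- Day 1-7 (mean k = 3): 1 - 48/366 = 86.9%
- Day 1-21 (mean k = 10): 1 - 132/366 = 63.9%
- Day 1-35: k now exceeds 28, so sum M(M - 1)/2 over months: (7 × 465 + 4 × 435 + 406)/(366 × 35) = 5,401/12,810 = 42.2%

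The same method for the 14 days after EOT, when AEs are collected by one telephone call:

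- EOT on Day 7 (Day 8-21, mean k = 13.5): 1 - 174/366 = 52.5%
- EOT on Day 14 (Day 15-28, mean k = 20.5): 1 - 258/366 = 29.5%
- EOT on Day 21 (Day 22-35, summed directly): (7 × 45 + 4 × 36 + 28)/5,124 = 9.5%

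**How visible the error is.** For Day 1-21, 21 × (366 - 12) - 12 × 210 = 4,914 of 7,686 onsets are moved. Those landing before Day -3 need Day 1 on the 6th or later: 21 × (366 - 60) - 12 × 210 = 3,906. So 3,906/4,914 = 79.5% would precede the earliest possible consent visit.

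**Steroid stop, day missing.** For a course of L days with a complete start date, the stop lies L - 1 days after the start. The stop precedes the start in 1 - 12L/366 of cases: 77.0% (L = 7), 54.1% (L = 14), 31.1% (L = 21).

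**Steroid start, day missing.** The course is lengthened by the mean day-of-month offset, 5,401/366 = 14.8 days. Courses of 7, 14 and 21 days average 21.8, 28.8 and 35.8 days.

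**With a first-dose floor for AE onset.** None of the 12,810 Day 1-35 onsets is moved before first dose.

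**The case against.** The strongest objection is that the trigger may never occur. Subjects are inpatients until EOT. Protocol 6.2 requires records of co-administered and rescue treatment for each subject, and note 17 to the schedule of events includes mometasone, clobetasol and prednisone in accountability. Protocol 8.4.1 requires an AE onset date, and Protocol 13.1 requires queries to be resolved before the eCRF is approved. All of this stands, and it is why the point is minor. Missing days are most plausible for AEs after discharge ("All subjects will be contacted via telephone 14 days ±3 days after EOT visit to assess safety"), but that call reviews ongoing AEs, many of which would already have an onset recorded in hospital.

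It can also be said that a TEAE is defined by when the event occurred, not by an imputed date, and that most moved onsets would look impossible in a six-subject listing. That is fair, but the SAP states no handling for such a record, so the decision would be improvised. The mock tables (SAP section 18) are not readable in the public copy, so a footnote convention cannot be excluded.

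A reader might infer more than the documents support:

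- **That this trial's TEAE counts or steroid totals are wrong.** Nothing shows that any partial date exists. The percentages describe hypothetical records.
- **That adverse events are lost.** They remain in the listings, and serious ones in a separate listing.
- **That a rescue analysis is distorted.** A partial rescue start could give a zero or negative time, but "Time to rescue therapy will be presented in a listing" and no summary uses it.
- **That pre-admission steroid use corrupts cumulative exposure.** Eligibility is open-ended here ("lesion-only treatment for any amount of time with any topical steroids prior to screening is allowed without restriction"), and the endpoint wording, "Evaluation of total cumulative steroid exposure at baseline, by treatment week and at disease control", hints at prior use. But SAP 11.4 only lists prior topical steroids, SAP 10.1 calls Section 13 an abridged plan, and SAP 13.7 does not say that its total includes prior use.

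**Conclusion.** The concern holds as a defect in a stated rule, at minor priority. Where it is triggered, SAP 10.4 gives a wrong TEAE classification for about two thirds of Day 1-21 onsets (42% over Day 1-35), and an impossible steroid duration for 31% to 77% of courses, depending on length. These shares are conditional on a missing day and rest on uniform Day 1 and onset dates. They say nothing about how often a day is missing, which is probably rarely or never. The conclusion is limited to the readable SAP text.

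**What to change.** 1. **AE onset.** If the known part of the date matches first dose, impute the first-dose date and count the AE as treatment-emergent, unless its stop date shows that it ended before first dose.
2. **Steroid records still partial after queries.** Require start on or before stop. Floor any on-study start, mometasone or rescue, at Day 1. Impute a partial on-study stop to the last day of the known month or year, capped at the EOT/disease-control date. Flag these records in the listing and show the total under the earliest possible stop as a sensitivity value.
3. **Opening sentence of SAP 10.4.** Limit the statement that there is no imputation to non-date data.
4. **Prior use.** State whether SAP 13.7 includes it. A partial-date rule is needed only if it does.

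**Cost.** A few SAP lines and minor programming. A screening AE (Day -3 to 0) with no day and no stop date would usually count as a TEAE: 1 - 12 × 2.5/366 = 91.8%, the conservative direction. The stop cap is exact for a course that ran to EOT but overstates one that ended earlier: a 7-day course averages 13.1 days with EOT on Day 14 and 17.6 with EOT on Day 21, against 1.7 under the earliest possible stop. The Day 1 floor reduces a missing-start error without always removing it: a rescue course on Days 8-14 averages 13.1 days, against 21.8 as the rule stands and a true 7. Separating on-study from prior records assumes that the Steroid Treatment form allows it. SAP 13.3 names only the rescue category.
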